### 10.2.2. Severity/Intensity

For both adverse events and serious adverse events, the Investigator must assess the severity/intensity of the event.

The National Cancer Institute-Common Terminology Criteria for Adverse Events (CTCAE) Version 5.0 should be used to grade the severity/intensity of all events. These criteria will be provided in the Site Operations Manual. If a CTCAE criterion does not exist, the Investigator should grade the severity according to the following criteria:

- Grade 1 (mild): does not interfere with the patient's usual function
- Grade 2 (moderate): interferes to some extent with patient's usual function
- Grade 3 (severe): interferes significantly with patient's usual function
- Grade 4 (life-threatening): results in a threat to life or in an incapacitating disability
- Grade 5 (death): results in death

The term "severe" is often used to describe the intensity of a specific event (as in mild, moderate or severe myocardial infarction); the event itself, however, may be of relatively minor medical significance (such as severe headache). This criterion is not the same as "serious" which is based on patient/event outcome or action criteria associated with events that pose a threat to a patient's life or functioning.

Seriousness, not severity, serves as a guide for defining regulatory obligations.

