## 7.3. Patient Withdrawal Criteria

All patients are free to withdraw from participation in the study at any time, for any reason, and without prejudice. The Investigator must withdraw any patient from the study if the patient requests to stop participating in the study. The Investigator, Sponsor, or its designee may remove a patient from the study at any time and for any reason. In addition, patients must be withdrawn if they:

- Have a prior history of thrombotic event(s);
- Experience a thromboembolic event;
- Experience an intolerable adverse event, including but not limited to bone marrow related events characterized by protocol specified hematologic abnormalities, or a  $\geq$  Grade 3 cardiac event, or a  $\geq$  Grade 4 (other) adverse event (CTCAE v5.0 criteria) considered possibly related to study drug. Because laboratory abnormalities can occasionally occur that do not in themselves pose an unacceptable risk to subject safety (e.g., CK elevations with exercise, laboratory errors or artifacts), the occurrence of a  $\geq$  Grade 4 laboratory abnormality, or any laboratory abnormality of concern to the Investigator, will be discussed with the Medical Monitor and a determination will be made, based on a reassessment of risk-benefit for the subject, whether the subject should discontinue randomized treatment. Documentation on the determination will be maintained in the study files;
- Require a medication that is prohibited by the protocol. However, under certain circumstances, and in consultation with the Medical Monitor, short-term use of a

prohibited medication may not necessitate withdrawal when its use is unlikely to unfavorably alter the risk-benefit of subject participation or confound the study endpoints;

- Experience an adverse event of progressive multifocal leukoencephalopathy (PML) or skin cancer which are rare but potential risks of the drug;
- Do not follow guidelines specified in the protocol (i.e., is noncompliant with protocol procedures or study treatment administration);
- In the opinion of the Investigator, have any medically appropriate reason or significant protocol violation;
- Become pregnant;
- Have a serious adverse event associated with a SARS-CoV-2 infection;
- Are lost to follow up;
- Are, in the judgement of the Investigator, not exhibiting clear benefit following one full year of active treatment with CTP-543;

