## 10. ADVERSE EVENTS

### 10.1. Definition of Adverse Event

An adverse event is any untoward medical occurrence that may appear or worsen in a patient during the course of a study. It may be a new intercurrent illness, a worsening concomitant illness, an injury, or any concomitant impairment of the patient's health, including laboratory test values, regardless of etiology. Any worsening (i.e., any clinically significant adverse change in the frequency or intensity of a pre-existing condition) should be considered an adverse event. A diagnosis or syndrome should be recorded on the adverse event page of the eCRF rather than the individual signs or symptoms of the diagnosis or syndrome. A worsening of the condition under study, alopecia areata, will not be reported as an adverse event.

All patients will be monitored for adverse events during the study. Assessments may include monitoring of the following parameters: the patient's clinical symptoms, laboratory, physical examination findings, or findings from other tests and/or procedures.

An adverse event reported after informed consent, but before the first dose of study drug (i.e., Day 1), will be considered a pretreatment adverse event and will be captured on the eCRF. Adverse events will be considered treatment-emergent if the onset is after the first dose of study drug or if an ongoing Adverse Event worsens after dosing is initiated.

An abnormal laboratory value is considered to be an adverse event if the abnormality:

- results in discontinuation from the study;
- is judged by the Investigator to be of significant clinical importance requiring treatment, modification/interruption of investigational product dose, or any other therapeutic intervention

Regardless of severity grade, only laboratory abnormalities that fulfill a seriousness criterion need to be documented as a serious adverse event.

If a laboratory abnormality is one component of a diagnosis or syndrome, then only the diagnosis or syndrome should be recorded on the adverse event eCRF. If the abnormality was not a part of a diagnosis or syndrome, then the laboratory abnormality should be recorded as the adverse event. If possible, the laboratory abnormality should be recorded as a medical term and not simply as an abnormal laboratory result (e.g., record thrombocytopenia rather than decreased platelets).

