#### **11.2.3.1. Adverse Events**

Treatment-emergent adverse events (TEAEs) will be defined as any adverse event that occurs after administration of the first dose of study drug until completion of the study or the Early Termination Visit. The number and percentage of patients who report TEAEs will be summarized by system organ class and preferred term.

Treatment emergent adverse events will also be summarized by intensity as well as relationship to study drug.

Patients who report the same preferred term on multiple occasions will be counted once for the preferred term: under the highest severity when summarized by severity and under the closest relationship to study drug when summarized by relationship. If a patient reports multiple preferred terms for a system organ class, the patient will be counted only once for that system organ class.

The number and percentage of patients who experience TEAEs will be summarized by dosing regimen for the following:

- By system organ class and preferred term
- By severity/intensity, system organ class, and preferred term
- By relationship to study drug, system organ class, and preferred term
- Serious adverse events by system organ class and preferred term
- Serious adverse events by relationship to study drug, system organ class, and preferred term

- Adverse events resulting in discontinuation of study drug by system organ class and preferred term
- Adverse events that result in study drug dose interruption by system organ class and preferred term

By-patient listings will be provided for any deaths, serious adverse events, and adverse events leading to discontinuation of treatment.

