An overall TEAE summary table by treatment group and overall with the total number of TEAEs and the number and percentage of subjects with at least one of the following will be presented: TEAE, serious TEAE, serious related TEAE, TEAE leading to study drug interruption, TEAE leading to dose reduction, TEAE leading to study discontinuation, TEAE leading to death, mild TEAE (CTCAE grade 1), moderate TEAE (CTCAE grade 2), severe TEAE (CTCAE grade 3 or above), mild related TEAE (CTCAE grade 1), moderate related TEAE (CTCAE grade 2), severe related TEAE (CTCAE grade 3 or above), related TEAE, possibly related TEAE, probably related TEAE, definitely related TEAE, not related TEAE, unlikely related TEAE, related serious TEAE, possibly related serious TEAE, probably related serious TEAE, definitely related serious TEAE, not related serious TEAE, unlikely related serious TEAE. “Related” TEAEs will be defined as TEAEs which the study investigator has categorized as possibly, probably, or definitely related to study drug. “Not related” TEAEs will be defined as TEAEs which the study investigator has categorized as unlikely or not related to study drug. “Related” serious TEAEs and “not related” serious TEAEs will be defined analogously for serious TEAEs. For each severity category, the subject will be counted once at the subject’s maximum level of severity. For each relatedness category, subjects will be counted once at the subject's maximum level of relatedness.

The number and percentage of subjects who experience TEAEs and the total number of TEAEs will be summarized by treatment group and overall for the following:

- By system organ class and preferred term
- By severity/intensity (mild [CTCAE grade 1], moderate [CTCAE grade 2], or severe [CTCAE grade 3 or above]), system organ class, and preferred term
- By maximum severity/intensity (mild [CTCAE grade 1], moderate [CTCAE grade 2], or severe [CTCAE grade 3 or above]), system organ class, and preferred term
- By relationship to study drug, system organ class, and preferred term

Sun Pharmaceutical Industries, Inc.
Statistical Analysis Plan – CP543.5002

- By maximum relationship to study drug, system organ class, and preferred term
- Serious TEAEs by system organ class and preferred term
- Serious TEAEs by relationship to study drug, system organ class, and preferred term
- Serious TEAEs by maximum relationship to study drug, system organ class, and preferred term

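### SAP 9.3 pools CTCAE Grades 3, 4 and 5 as severe, so no adverse-event summary it describes counts the patients per dose whose worst event was Grade 4

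*Protocol*

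**What the plan says.** Protocol 10.2.2 has every AE graded by CTCAE version 5.0. Where CTCAE has no criterion, the investigator uses a five-level list that runs from mild through moderate and severe to "Grade 4 (life-threatening): results in a threat to life or in an incapacitating disability" and "Grade 5 (death): results in death". Protocol 11.2.3.1 then plans a TEAE table described as "By severity/intensity, system organ class, and preferred term", without saying how many grade categories it will have.

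SAP 9.3 settles the categories: mild is Grade 1, moderate is Grade 2, and everything higher falls in one class, labelled in the overall summary as "severe TEAE (CTCAE grade 3 or above". The same three classes are used for related TEAEs in the overall summary, and for both tables by system organ class and preferred term (by severity and by maximum severity).

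Protocol 7.3 treats the upper grades differently from one another. Withdrawal is required from "Grade 3 cardiac event" upwards for cardiac events, and from "Grade 4 (other) adverse event (CTCAE v5.0 criteria) considered possibly related to study drug" upwards for the rest. Laboratory abnormalities of Grade 4 or more are handled separately: each "will be discussed with the Medical Monitor and a determination will be made" on whether the subject stops treatment.

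**The concern.** The protocol asks investigators to distinguish severe from life-threatening events, and the SAP summaries then merge them. Long-term safety is a stated objective of the study (Protocol 6). The 12 mg BID dose was discontinued after thrombosis reports (Protocol 6.1), and AEs are tabulated under the dose most recently taken (SAP 9.3). A reader of the report will therefore want to know how many patients on each dose had a life-threatening event as their worst. Under the SAP wording, a column made up wholly of Grade 3 events and a column with many Grade 4 events can print the same severe row. Grades 3 and 4 also do not carry the same weight in the protocol, because Protocol 7.3 gives them different consequences for non-cardiac events.

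**Working it through.** There is no sample-size, power or alpha figure to reproduce, because the study is descriptive. The check has two parts.

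**Can any summary in the SAP text supply the missing count?**

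| SAP output | What it shows | Gives Grade 4 by dose? |
|---|---|---|
| Overall TEAE summary, severity rows, all and related (9.3) | Grade 1, Grade 2, Grade 3 or above | No |
| By-severity and maximum-severity tables (9.3) | Same three classes | No |
| Fatal TEAE row (9.3) | Patients with a fatal TEAE | Isolates fatal events only |
| Serious-TEAE rows and tables (9.3) | Serious events, some split by relationship, none by grade | No |
| TEAEs leading to discontinuation, interruption or dose reduction (9.3) | Not split by grade | No |
| Potentially clinically significant laboratory values (9.5) | Grades 3 and 4 pooled; Grade 2 or higher for platelets | No |
| Blood pressure shifts and weight frequencies (9.6.1) | Individual CTCAE grades | For measured values, not AEs |
| AE listings (9.3, 9.4) | Every AE by subject | A listing, not a count by dose |

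The serious-TEAE tables come closest, but they differ from a Grade 4 count in both directions. Hospitalization can make an event serious whatever its grade (Protocol 10.2.1). Protocol 10.1 also says "Regardless of severity grade, only laboratory abnormalities that fulfill a seriousness criterion need to be documented as a serious adverse event", so a Grade 4 laboratory AE may be non-serious.

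**How tightly do the planned rows fix the count?** SAP 9.3 counts each subject once at maximum severity. Within one treatment column, let n3, n4 and n5 be the patients whose worst TEAE was Grade 3, 4 or 5. Assume every fatal TEAE is recorded as Grade 5. Then:

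- severe row: S = n3 + n4 + n5
- fatal row: D = n5
- so n4 = S − D − n3

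No row gives n3, so n4 can be anything from 0 to S − D. For related TEAEs the range is wider. The fatal row is not split by relationship, so with S_R patients in the related severe row, n4 lies between 0 and S_R unless the listings are consulted.

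Illustration with assumed counts (the documents fix no sample size): 150 patients in a column, S = 12, D = 0. The row prints 12 (8.0), since 12/150 = 8.0%. The Grade 4 share could be anywhere from 0/150 = 0% to 12/150 = 8.0%. Other rows, such as serious TEAEs, might hint at which, but they would not give the number.

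**The case against.** The strongest reply is that clinically important Grade 4 events are already visible. The protocol's own wording for Grade 4, a threat to life or incapacitating disability, overlaps closely with its seriousness criteria in 10.2.1. Serious TEAEs are tabulated by dose and by relationship, and blood dyscrasias are named there as an example of an important medical event. This stands in large part: what is wholly unseen in the serious tables is mainly non-serious laboratory AEs. It does not produce a Grade 4 count, because those tables are not split by grade and also contain lower-grade events.

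A second reply concerns the withdrawal rule. A reader might infer that the missing row hides how many patients met a mandatory Grade 4 withdrawal criterion. The documents do not support that. Protocol 7.3 uses Grade 4 only for non-cardiac events considered possibly related, sets Grade 3 for cardiac events, and sends Grade 4 laboratory abnormalities to individual review. A Grade 4 row would mix these groups and would not by itself count patients who met the rule. TEAEs leading to discontinuation are tabulated in any case.

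A reader might also infer an undeclared departure from the protocol, because SAP 12 does not list the pooling. That is not shown. Protocol 11.2.3.1 asks for a table by severity and promises no particular number of rows, and Protocol 11 leaves technical detail to the SAP. Choosing display categories can fairly be seen as such detail.

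Finally, the mock tables are attached separately (SAP 4.1) and were not available, so the point can be made only about the tables as the SAP text describes them.

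**Conclusion.** The point holds as a reporting gap. As SAP 9.3 is written, no AE summary gives the number of patients per dose whose worst event was Grade 4, and the planned rows bound it only between 0 and S − D. The real loss is the split between Grade 3 and Grade 4, since deaths can be read from their own row. No estimate is biased, no error rate is involved, and the grades remain in the database and listings. The conclusion rests on two assumptions: that the table shells follow the three categories in the SAP text, and that fatal TEAEs are graded 5. How many patients are affected cannot be estimated from the documents. This is a cheap improvement worth making, not a defect that threatens the study's conclusions.

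**What to change.** In SAP 9.3, replace the single Grade 3 or above class with separate Grade 3, Grade 4 and Grade 5 rows, and keep Grade 3 or above as a subtotal so that the currently planned figure is still reported. Do this at least in the overall TEAE summary, for all and for related TEAEs, and in the maximum-severity table. Extending it to the by-severity table is optional. Do not label the Grade 4 row as a count of patients meeting the withdrawal criteria.

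The cost is SAP wording and table shells. Protocol 10.2.2 already requires a grade for every event, so no new data are needed. The downside is a few extra rows, most of them sparse.

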### 10.2.3. Relationship to Study Drug

Relationship should be assessed and provided for every adverse event/serious adverse event based on currently available information. Relationship is to be reassessed and provided as additional information becomes available. Adverse events will be classified by the Investigator as follows:

**Definitely Related:** There is clear evidence to suggest a causal relationship, and other possible contributing factors can be ruled out. The clinical event, including an abnormal laboratory test result, occurs in a plausible time relationship to drug administration and cannot be explained by concurrent disease or other drugs or chemicals. The event resolves or improves upon withdrawal of drug (de-challenge). The event would be considered as definitely related to the study drug upon results of a positive re-challenge procedure.

**Probably Related:** There is evidence to suggest a causal relationship (e.g., the event occurred within a reasonable time after administration of the trial medication). However, the influence of other factors that may have contributed to the event (e.g., the patient's clinical condition, other concurrent disease, concomitant medications or events) is unlikely, and the event follows a clinically reasonable response upon withdrawal of drug (de-challenge).

**Possibly Related:** There is evidence to suggest a causal relationship (e.g., the event occurred within a reasonable time after administration of the study drug). However, the influence of other factors may have contributed to the event (e.g., the patient's clinical condition, other concurrent disease, concomitant medications or events).

**Unlikely Related:** A clinical event, including an abnormal laboratory test result, whose temporal relationship to drug administration makes a causal relationship improbable (e.g., the event did not occur within a reasonable time after administration of the trial medication) and in which

other drugs or concurrent or underlying disease provide plausible explanations (e.g., the patient's clinical condition, other concomitant treatments).

**Not related:** The adverse event is completely independent of study drug administration, and/or evidence exists that the event is definitely related to another etiology. There must be an alternative, definitive etiology documented by the clinician.

#### **10.2.4. Duration**

For all adverse events whether or not considered serious, the Investigator will provide a record of the start and stop dates of the event. Every effort should be made to resolve all adverse events with continued follow-up with the patient until appropriate resolution can be achieved. If an event is unresolved at the end of the study it will be recorded as ongoing.

#### **10.2.5. Action Taken**

The Investigator will record the action taken with investigational product as a result of an adverse event or serious adverse event on the eCRF, as applicable (e.g., discontinuation, or interruption of investigational product, as appropriate) and record if concomitant and/or additional treatments were given for the event.

#### **10.2.6. Outcome**

The Investigator will record the outcome of adverse events on the eCRF, as applicable (e.g., recovered, recovered with sequelae, not recovered, or death (due to the adverse event)).

### **10.3. Follow-Up**

Adverse events, severe adverse events and serious adverse events, including clinically significant laboratory tests, electrocardiograms, or physical examination findings, will be followed, regardless of causality, for as long as necessary to adequately evaluate the patient's safety, or until the event stabilizes, is otherwise explained, death occurs, or the patient is lost to follow up. If resolved, a resolution date should be provided. The Investigator is responsible for ensuring that follow-up includes any supplemental investigations indicated to elucidate the nature and/or causality of the adverse event. This may include additional clinical laboratory testing or investigations, examinations, or consultation with other health care professionals as is practical.

### **10.4. Pregnancy**

The Sponsor must be informed within 24 hours upon learning that a patient, or male patient's partner, has become pregnant any time after the first dose of study drug until 30 days after the last dose of study drug. Prior to any data collection for a pregnant participant or a pregnant partner of a participant in study CP543.5002, written informed consent on the pregnant partner/participant information and consent form must be provided by the study participant or the partner of the participant, in accordance with local practice, law or regulation. Information about the follow-up of the pregnancy will be explained to the pregnant participant or the pregnant partner of a participant. A copy of the pregnant partner/participant information and consent form must be given to the patient, if applicable.

While pregnancy itself is not considered an AE or SAE, pregnancy reports will be processed in accordance with the same procedures set forth for non-expedited SAEs. The Pregnancy Notification eCRF in EDC should be used to report the pregnancy to the Sponsor or its designee. Patient pregnancies (or pregnancy of a male patient's partner) must be followed until termination

of pregnancy or the birth of the child via a pregnancy notification. The Pregnancy Outcome eCRF should be used to report information regarding the status of the infant. No mandatory visits, tests, or specific assessments are required for this study. However, the Principal Investigator will liaise regularly with the health care provider of the participant or with the health care provider of the partner until termination of the pregnancy or until the birth of the child. Follow-up of the pregnancy will be scheduled by the study participant or the partner of the participant with their health care provider and conducted according to the standard of care. Standard of care is defined as a diagnostic and customary clinical treatment/practice process that a clinician chooses according to their clinical judgement for a certain type of illness, or clinical circumstance based on the clinical practice guidelines. The Clinical Research Organization (CRO) responsible for pharmacovigilance will contact the investigative site, advise them to follow the pregnancy, and query the site to report any complications during the pregnancy, or any adverse pregnancy outcomes.

The pregnancy eCRF pages are completed in EDC, and require the site report any clinical finding on prenatal testing. The obstetrical history is also collected. The Principal Investigator advises the participant to call the site to report any complications. In addition, the CRO pharmacovigilance group will query the site after the determined due date to obtain final pregnancy and newborn outcome.

Pregnancy cases are not considered closed until all data fields on the pregnancy report form are properly completed, including pregnancy outcome. Information on the outcomes of pregnancies will be reported along with all other safety data from the study in the final study report. In addition, a database of information relating to reported pregnancies across all CTP-543 studies will be maintained in order to include these data in any subsequent marketing application.

If pregnancy occurs in a female patient, then study drug should be discontinued immediately. If a female partner of a male patient taking investigational product becomes pregnant, the male patient taking the investigational product should notify the Investigator, and the pregnant female partner should be advised to call her healthcare provider immediately.

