### 7.1. Patient Inclusion Criteria

1. Written informed consent, and authorization for release and use of protected health information.
2. Have completed a 24-week Treatment Period in a previous qualifying CTP-543 clinical trial.
3. Female subjects are eligible to participate if at least one of the following conditions applies:
  - a) Is a woman of childbearing potential (WOCBP) and using a medically highly effective form of birth control with a failure rate less than 1% per year from at least 4 weeks prior to Baseline until at least 30 days following last dose of study drug.  
Examples of medically highly effective birth control methods include:
    - i. Combined (estrogen and progestogen containing) hormonal contraception (oral, patch, vaginal ring)
    - ii. Progestogen-only hormonal contraception associated with inhibition of ovulation (oral, injectable, implantable)
    - iii. Intrauterine device or intrauterine hormone-releasing system
    - iv. Bilateral tubal occlusion
    - v. Vasectomized partner (partner is the sole sexual partner of the WOCBP trial participant and the vasectomized partner has received medical assessment of the surgical success)
    - vi. Sexual abstinence (reliable as refraining from heterosexual intercourse during the above-mentioned period)
  - b) Is not a WOCBP:
    - i. Premenopausal with one of the following:
      - a. Documented hysterectomy;
      - b. Documented bilateral salpingectomy;
      - c. Documented bilateral oophorectomy.
    - ii. Postmenopausal (cessation of menses for at least 12 months prior to screening)  
Postmenopausal is defined as no menses for 12 months without an alternative medical cause. In addition, a high follicle stimulating hormone (FSH) level in the postmenopausal range may be used to confirm postmenopausal in women under 60 years old and not using hormonal contraception or hormone replacement therapy (HRT). However, in the absence of 12 months of amenorrhea, a single FSH measurement is insufficient. Females on HRT and whose menopausal status is in doubt will be required to use one of the nonestrogen hormonal highly effective contraception methods if they wish to continue their HRT during the study. Otherwise, they must discontinue HRT to allow confirmation of postmenopausal status before study enrollment
4. Male participants must:

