- a. Agree to use, with their partners, male contraception (condom) and one of the highly effective contraceptive methods listed in Inclusion Criterion 5, from Baseline until at least 90 days following last dose of study drug.
- b. Refrain from donating sperm during the study and for at least 90 days after the end of the study.

5. Willing to comply with the study visits and requirements of the study protocol.

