## **10.6. Reporting Adverse Events**

The Investigator must report to Sponsor or its designee all adverse events that occur during the study from the time written informed consent is given until the final study visit or early termination, regardless of their relationship to the study drug. Serious adverse events and pregnancies will be reported from the time written informed consent is given through 30 days beyond the last dose of study drug.

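### Partner pregnancies need be reported only to 30 days after the last dose, although male contraception is required for at least 90 days, leaving post-dose days 31-90 uncovered

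*Protocol*

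**What the plan says.** Four parts of the protocol bear on this.

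- **Notification (Section 10.4).** The Sponsor must be informed within 24 hours of the site learning of a pregnancy in a patient or a male patient's partner. The qualifying period is "any time after the first dose of study drug until 30 days after the last dose of study drug".
- **Reporting (Section 10.6).** "Serious adverse events and pregnancies will be reported from the time written informed consent is given through 30 days beyond the last dose". No separate period is given for partners.
- **Contraception (Section 7.1).** For women of childbearing potential, criterion 3a sets the period as "from at least 4 weeks prior to Baseline until at least 30 days following last dose of study drug". For men, criterion 4a sets it as "from Baseline until at least 90 days following last dose of study drug". The Synopsis repeats both. Criterion 4b also bars sperm donation for at least 90 days after the end of the study.
- **Instruction to men (end of Section 10.4).** If a partner becomes pregnant, "the male patient taking the investigational product should notify the Investigator".

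Section 10.4 also commits the Sponsor to report pregnancy outcomes in the final study report, and says that "a database of information relating to reported pregnancies across all CTP-543 studies will be maintained" for use in later marketing applications. The SAP has no rule for partner pregnancies; its Section 9.5 only lists pregnancy test results.

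**The concern.** By asking men to prevent conception for at least 90 days, the protocol treats that whole period as one of possible risk. It then requires reports for only the first 30 of those days. The limit appears to have been set from the female contraception period and applied to partners without adjustment.

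What is at stake is the completeness of the pregnancy record. If the cross-study database holds no partner pregnancies from post-dose days 31-90, a reader cannot tell whether none occurred or whether none had to be reported. Voluntary reports may still arrive, but they would be incomplete and possibly selective.

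**Working it through.** The plan states no figure to reproduce, so the check compares the time windows and then sizes the gap.

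**1. End of each window, in days after the last dose**

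| | Contraception ends | Pregnancy reporting ends | Gap |
|---|---|---|---|
| Female patients | at least 30 (criterion 3a) | 30 (Sections 10.4, 10.6) | 30 − 30 = 0 |
| Partners of male patients | at least 90 (criterion 4a) | 30 (Sections 10.4, 10.6) | 90 − 30 = 60 |

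The uncovered period is post-dose days 31-90.

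**2. Does other text close the gap?**

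- The closing paragraph of Section 10.4 gives men no end date for telling the Investigator. It is worded for a man who is taking the product, so it does not clearly reach one who stopped 31 to 90 days earlier. It also leaves the limits on reporting to the Sponsor unchanged.
- The requirement in Section 10.4 to follow pregnancies to birth or termination has no day limit. It governs pregnancies already notified and does not widen the notification period.
- The only item in either Schedule of Events table after the final visit is the 4-week home urine pregnancy test, which does not apply to men.

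None of these extends partner reporting past day 30.

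**3. Share of the male contraception period, from Baseline**

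- 52 weeks of treatment: 52 × 7 + 90 = 364 + 90 = 454 days; 60/454 = 13.2%.
- 108 weeks of treatment: 108 × 7 + 90 = 756 + 90 = 846 days; 60/846 = 7.1%.

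These are shares of calendar time, not of risk. All treatment time and the first 30 post-dose days are covered.

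**4. Expected partner pregnancies in the 60 days, per 100 men with a fertile partner**

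Formula: 100 × annual pregnancy rate × 60/365.

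- At 1% per year, the protocol's ceiling for a highly effective method: 100 × 0.01 × 60/365 = 0.16.
- At 10% per year, an assumption for lapsed contraception that is not in the documents: 100 × 0.10 × 60/365 = 1.6.

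The result is proportional to the rate, so each additional percentage point per year adds about 0.16 per 100 men. The documents do not give the number of male patients, so no absolute count can be derived.

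**The case against.** The strongest reply is that this is a choice, not a contradiction. Contraception prevents risk and reporting captures data; nothing says the two periods must be equal, and a site can comply with both. The protective measure runs its full 90 days. Nonclinical detail is left to the Investigator's Brochure, so the documents do not show whether days 31-90 carry exposure that matters for a partner's pregnancy. That stands as a limit on the point's weight. It does not explain why the protocol guards a period that it does not require anyone to report on.

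Second, the numbers are tiny. Criterion 4a requires a condom as well as a highly effective method, so the expected number with full compliance is below even 0.16 per 100. The 10% rate is unsourced and supposes that every man lapses. Both remarks are fair.

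Third, Section 10.4 dates the limit by when the pregnancy arises, not when it is discovered. A pregnancy beginning by day 30 and learned of on day 60 is within its notification rule. This is correct, and it confines the gap to pregnancies that begin after day 30.

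Fourth, a wording change alone depends on men volunteering information after they have left the study. It would also come late for some patients: the Synopsis estimates last-patient completion in July 2024, and the current text post-dates the urgent safety measure. This lowers the expected yield, but does not remove the mismatch.

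**Conclusion.** The concern holds. Following the protocol exactly leaves partner pregnancies that begin on post-dose days 31-90 with no reporting duty, for a period of 60 days in which men must still use contraception. Female patients have no corresponding gap.

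The textual mismatch is certain. Its practical size is small and rests on the assumed pregnancy rates, the proportion of men with fertile partners, and a number of male patients that is not given. The effect is confined to the pregnancy safety record: no efficacy result and no planned SAP summary would change. It is an improvement to consider, not a threat to the trial's conclusions.

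**What to change.** - In Sections 10.4 and 10.6, set the reporting period for pregnancies in male patients' partners to 90 days after the last dose. Keep 30 days for female patients.
- Reword the closing paragraph of Section 10.4 so that men are told to notify the site of any partner pregnancy through 90 days after the last dose, whether or not they are still taking study drug.
- In the same edit, align the start of the window, which is first dose in Section 10.4 but consent in Section 10.6. Also correct the cross-reference in criterion 4a of Section 7.1, which points to Inclusion Criterion 5 for the contraceptive methods; the Synopsis correctly points to Criterion 3.

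The cost is wording changes in the protocol, the consent form and the instructions to male patients, plus a few extra pregnancy reports at most. Unless the change is classed as administrative, Section 12.4 requires Ethics Committee approval before it takes effect. The partner consent form, pregnancy eCRFs and follow-up process already exist. Active capture, as opposed to reliance on men coming forward, would need one added contact at about day 90.
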